#### 4.3.4. Follow-Up Schedule

Follow-up visits for treatment and control patients will occur according to the following schedule: Visits at 1 week, 2 weeks, and 4 weeks ( $\pm$  3 days), and thereafter every 4 weeks ( $\pm$  2 weeks) until primary endpoint assessment at 32 weeks. In addition, 1-2 weeks after the adjustment procedure the subject will have a follow up appointment with the PI/NP.

Each follow-up visit will include:

1. Clinical assessment by PI or nurse practitioner or physician’s assistant for both the treatment group and control group (*Appendix E6: CRF6\_Control Group PI Follow Up* or *Appendix E7: CRF7\_Treatment Group PI Follow Up*)
2. Satiety and Dietary Assessment for both the treatment group and control group - limited to 30-45 minutes per session (*Appendix E8: CRF8\_Control Group Dietician Follow Up* or *Appendix E9: CRF9\_Treatment Group Dietician Follow Up*)
3. Record adverse events, device complications, concomitant medication (*Appendix E6: CRF6\_Control Group PI Follow Up* or *Appendix E7: CRF7\_Treatment Group PI Follow Up*)
4. Weight to be done by staff (patient may not speak with weighing personnel and may not disclose if they are control or treatment arm)

Control patients will exit the study at Week 32. Treatment patients will have the device explanted and will be followed for an additional 24 weeks according to the following schedule: Visits at Week 36 ( $\pm$  3 days) and thereafter every 4 weeks ( $\pm$  2 weeks) until 56 weeks. Treatment patients who undergo balloon extraction prior to 32 weeks will be followed from the time of balloon extraction an additional 24 weeks according to the following schedule: Visits at 4 Weeks post extraction ( $\pm$  3 days) and thereafter every 4 weeks ( $\pm$  2 weeks) until 24 weeks after the extraction.

These follow-up visits for the treatment group only, will include:

1. Clinical Assessment - only at the visit 4 weeks post extraction(*Appendix E7: CRF7\_Treatment Group PI Follow Up*)
2. Satiety and Dietary Assessment (*Appendix E9: CRF9\_Treatment Group Dietician Follow Up*)

A summary of required visits and procedures for subjects who do not require an unscheduled endoscopy is shown in the following table and provided in *Appendix B: Study Visits and Master Schedule*:

Assessment / Procedure	Screening Assessments	7 Days Prior to implant	Implantation	Adjustment	Explantation	Follow-Up Assessment weeks 1-32	WEEKS 36 - 56
Informed Consent	X						
Date of birth/gender	X						
Body Weight	X	X	X	X	X	X	X
Body Height	X						
BMI	X	X	X			X* (week 32)	X * (week 56, or 24 weeks after extraction)
Ideal weight/ Excess Weight	X				X	X* (week 32)	X * (week 56, or 24 weeks

Assessment / Procedure	Screening Assessments	7 Days Prior to implant	Implantation	Adjustment	Explantation	Follow-Up Assessment weeks 1-32	WEEKS 36 - 56
							after extraction)
Medical History	X						
Physical Exam 	X			X	X		Week 36, or 4 weeks after extraction
Blood Pressure	x		X	X	X	X	Week 36, or 4 weeks after extraction
CBC  Coag  (Coag @ screen only)	X						Week 36, or 4 weeks after extraction
H. Pylori Serology	X						
Chemistry Panel 	X						X Week 36, or 4 weeks after extraction
HgbA1C2 IF DIABETIC	X						X Week 36, or 4 weeks after extraction
EKG*(Females and Males >40 y/o	X						
Psychological Evaluation	X						
Inclusion and Exclusion Criteria	X						
Develop/Review Dietary Plan	X						
Satiety and Dietary Assessment						X	X (or 24 weeks after extraction)
Investigator or Nurse follow up				X	X	X	X (or 24 weeks after extraction)
Medications List	X	X				X	X Week 36, or 4 weeks

 Investigator or co-investigator must perform physical exam.

 See section 4.3.1 for required tests

Assessment / Procedure	Screening Assessments	7 Days Prior to implant	Implantation	Adjustment	Explantation	Follow-Up Assessment weeks 1-32	WEEKS 36 - 56
							after extraction
Urine Pregnancy Test women of child bearing potential*	X	X					
Adverse Events/Device Complications			X	X	X	X	X
Verify Birth Control for Females	X						

#### 4.4. Participant Retention

All patients will be encouraged to complete study follow-up, and all reasonable efforts will be made to ensure completeness of follow-up

It is understood that study participants may withdraw consent for study participation at any time irrespective of their reasons. The investigators may also withdraw a recipient from the study in order to protect their safety and/or if they are unwilling or unable to comply with the required study procedures.

In the event of a patient withdrawing from the trial, the reason for withdrawal must be documented on the CRF.

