### 4.2. Blinding/Masking

Although it is not possible to blind the study subject or the investigator to the treatment group, weight measurements are to be performed by clinical staff who are blinded to the treatment group. Subjects will be instructed not to speak with weighing personnel and to not disclose if they are control or treatment arm.

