## 7. STATISTICS

### 7.1. Description of Statistical Methods

#### 7.1.1. Study cohorts for analyses

The primary analysis will be based on the intent-to-treat dataset, which will include all randomized subjects according to their randomized treatment. However, any subject with an absolute contraindication to balloon implantation which was only revealed at the endoscopy procedure, and who therefore did not receive a balloon, will not be considered in analysis of efficacy.

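### Section 4.4 lets unblinded investigators withdraw subjects from the study for non-compliance without requiring a Week 32 weight, which risks avoidable informative missing data in both co-primary endpoints

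*Combined protocol and SAP*

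**What the plan says.** Section 4.4 (Participant Retention) states: "The investigators may also withdraw a recipient from the study in order to protect their safety". It adds a second ground: "if they are unwilling or unable to comply with the required study procedures". No threshold is given, and stopping treatment is not distinguished from leaving the study. The same section promises that "all reasonable efforts will be made to ensure completeness of follow-up" and requires the reason for withdrawal on the CRF. It does not say whether a subject withdrawn by the investigator is still weighed at Week 32.

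On masking, Section 4.2 says that "it is not possible to blind the study subject or the investigator to the treatment group", while "weight measurements are to be performed by clinical staff who are blinded to the treatment group".

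The primary analysis set in Section 7.1.1 is labelled intent-to-treat and "will include all randomized subjects according to their randomized treatment", apart from subjects found at endoscopy to have an absolute contraindication. Section 7.1.2 interpolates interim gaps and fills every other missing weight by regression-based multiple imputation (five datasets). The model contains baseline weight and BMI, gender, centre, arm and the recorded weights. Compliance and reason for withdrawal are not in it. LOCF is the only sensitivity imputation.

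Section 4.3.4 follows subjects for 24 weeks after an early balloon extraction, but Section 7.1.2 treats them as dropouts from the explant and does not use their later weights.

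**The concern.** A person who knows the assignment can end a subject's participation on a ground that plausibly relates to outcome. The required procedures include visits and dietary counselling, so subjects who do not comply may well lose less weight, or regain more, than compliant subjects with similar early weights. The imputation model cannot see that difference, because it does not know who was withdrawn or why. LOCF does not probe it either: it freezes the loss reached at withdrawal and misses later regain. No analysis under a missing-not-at-random assumption is planned.

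The second co-primary endpoint is the more exposed. It compares the device arm alone with a 50% goal, so no control arm offsets an optimistic imputation. The first co-primary endpoint is affected only through a difference between the arms.

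**Working it through.** **Plan's own figure.** Section 7.2 assumes mean %TBL of 10.34 (device) and 3.3 (control), SD 6.6, margin 4.5, one-sided 2.5%, 80% power and 2:1 allocation. The planned excess over the margin is 10.34 - 3.3 - 4.5 = 2.54. Control n = (1.96 + 0.84)² × 6.6² × 1.5 / 2.54² = 79.5, so 80 control and 160 device, 240 in all, with power 80.2%. Allowing for 15% dropout, 240 / 0.85 = 282.35, against 282 stated. The design reproduces.

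**Assumptions not in the documents.** The documents give neither the number of investigator withdrawals nor the outcomes of those subjects. I take a share f of 3-8% of the 188 device subjects (about 6 to 15), a true loss m0 of 3.3% down to 0%, and imputation to the device-arm mean. The last is a worst case, because the stated model also uses earlier weights.

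**Mean %TBL in the device arm.** Bias = f × (10.34 - m0).
- f = 0.03, m0 = 3.3: 0.03 × 7.04 = 0.21 points
- f = 0.08, m0 = 0: 0.08 × 10.34 = 0.83 points

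**Response rate in the device arm.** With normal %TBL and SD 6.6, P(loss ≥ 5%) is 0.791 at mean 10.34, 0.398 at 3.3 and 0.224 at 0. Bias = f × (0.791 - P0).
- 0.03 × (0.791 - 0.398) = 1.2 points
- 0.08 × (0.791 - 0.224) = 4.5 points

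For scale, the planned excesses are 2.54 points over the margin and 79.1 - 50 = 29.1 points over the goal.

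**Direction in the mean comparison.** Let wS and wC be the shares withdrawn in the device and control arms, and g the amount by which imputed %TBL exceeds the truth, taken as 2 to 7 points in both arms. Bias = (wS - wC) × g, and SE = 6.6 × √(1/80 + 1/160) = 0.904. Type I error is at a true difference of 4.5.

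| Device / control withdrawn | Bias (points) | One-sided type I error |
|---|---|---|
| 5% / 0% | +0.10 to +0.35 | 3.2% to 5.8% |
| 15% / 5% | +0.20 to +0.70 | 4.1% to 11.8% |
| 5% / 5% or 15% / 15% | 0 | 2.5% |
| 5% / 15% | -0.20 to -0.70 | 1.5% to 0.3% |

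**Responder test at the null.** True rate exactly 50%, n = 188, withdrawn share w with true response rate p, imputed at the observed rate. Apparent rate = (0.50 - w × p) / (1 - w).
- w = 5%: p = 0 gives 0.50 / 0.95 = 52.6%; p = 40% gives 0.48 / 0.95 = 50.5%. Type I error is 10.5% and 3.4%, against 2.5% nominal.
- w = 15%, which would use the whole dropout allowance on investigator withdrawals and is an extreme: apparent rate 58.8% to 51.8%, type I error 62% to 6.5%.

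**The case against.** A reader might infer that poor performers' weights are lost by rule. The documents do not support that. The clause is permissive, it stands beside a general promise of complete follow-up, it does not say weighing stops, and its criterion is procedural compliance rather than weight loss. The fault is a missing provision; the link to outcome is plausible but inferred.

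A reader might also infer that imputing these subjects contradicts the intent-to-treat label. It does not, since imputing missing outcomes for randomized subjects is compatible with that label. Nor does every lost non-responder raise the response rate: it rises only if imputation makes that subject a responder. Visits at Weeks 1, 2 and 4 and then every four weeks supply weights to the model, so poor loss seen before withdrawal is partly carried into the imputed value, and LOCF carries it forward too. What remains open is what happens after withdrawal.

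Three further points stand. Some subjects unwilling to attend would give no Week 32 weight under any wording, so a rewording recovers only part of the loss. Section 4.3.4 already follows early-extraction subjects. And Section 7.1.2 would still discard a weight taken after explant, so changing Section 4.4 alone would leave the device-arm analysis unchanged for any withdrawn subject whose balloon is removed; the documents do not say whether it would be. That limits a change to Section 4.4 alone but does not answer the gap.

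**Conclusion.** The concern holds as a gap in the retention rule. Unblinded investigators may withdraw subjects from the study for non-compliance, no Week 32 weight is required afterwards, and the planned analyses do not test the assumption that fills the gap.

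If withdrawn subjects do worse than imputed, the responder rate is biased toward the device. For the mean difference, a claim that the bias must favour the device is not supported: it is zero when the arms are alike and conservative when control loses more.

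The sizes of 0.2-0.8 points in mean %TBL and 1.2-4.5 points in response rate are upper bounds within the assumed 3-8% share and 0-3.3% true loss. The mean figure is the overstatement in the device arm, with no offset from control. At the planned effects this bias alone would not decide the trial. It matters if results fall near 4.5 points or 50%.

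**What to change.** 1. Reword Section 4.4 so that non-compliance is recorded as a protocol deviation under Section 6.4 and is not in itself a ground for ending data collection.
2. Separate stopping study treatment from leaving the study, and seek the Week 32 weight from every randomized subject unless consent is withdrawn.
3. State in Section 7.1.2 that Week 32 weights so collected are used in the analysis. For subjects explanted early, whose later weights are now discarded, use them at least in a sensitivity analysis.
4. Report investigator withdrawals by arm and reason; the reason is already captured on the CRF. A missing-not-at-random sensitivity analysis for both co-primary endpoints would be a useful addition.

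The cost is a formal amendment under Section 10.2 and a few more attempted weighings, mostly at a visit already scheduled. One exception: 24 weeks of follow-up after an extraction before Week 8 ends, nominally, before Week 32 (for example 4 + 24 = 28), so those subjects would need one added weighing. No treatment rule changes.

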#### 4.5. Definition of the End of the Trial

The trial will end after completion of the 56-week visit for the last subject treatment group subject enrolled in the trial and a final study report will be generated.

## 5. SPATZ 3 DEVICE

### 5.1. Device Description

#### 5.1.1. Spatz3

The Spatz3 device (Figure 2) consists of a balloon positioned around a curved catheter inside the balloon, and whose catheter continues and exits outside of the balloon. The external catheter houses the stretchable inflation tubing.

**Figure 2: Spatz3 Prior to Implant**

**Figure 3: Spatz3 during Implantation**

The Spatz3 balloon is wrapped by 6 silicone bands during shelf life, which gives it a tapered profile. The bands are removed using the “band-off” silicone pull strings prior to implantation.

Pull both silicone strings to the left to remove all bands

The valve is secured to the white catheter with “valve-hold.”

Valve Hold

Pushing Valve Hold into White catheter

Valve Hold inside white catheter

The balloon is secured to the scope with the insertion facilitator.

Insertion Facilitator (as supplied)

Dressed on distal tip of scope w/ balloon ready to be secured

[figure not shown]
[figure not shown]
Rolled over balloon (2 holes to be used to secure to scope)

Balloon secured and insertion facilitator secured to scope

The balloon is inflated, adjusted and deflated via connection to an extension tube which has a 3-way stopcock at its proximal end. The extension tube is connected to the valve for all procedures and is provided in the packaging along with a 60 ml syringe (section 4.3.3.2 for details of all procedures).

The stretchable inflation tube design of the Spatz3 device permits balloon volume adjustment at the time of placement, and at a later time. Initial balloon volumes range from 400 cc to 550 ml. The minimum and maximum balloon volumes will range from 300 ml (an initial balloon volume of 400 or 450 ml that has been adjusted down to 300 ml due to intolerance) to 900 ml (an initial balloon volume of 550 ml that has been adjusted upward to 900 ml due to lack of any balloon effect in the first 2 weeks after implantation).

**Figure 4: Inflation tube at rest****Figure 5: Inflation Tube partially stretched**

A retractable/stretchable silicone inflation tube allows the balloon to have its volume adjusted after initial insertion, while the balloon remains in the stomach (Figure 4 and Figure 5). The inflation tube is a 10cm long stretchable soft silicone tubing with an inner diameter of 2mm and an outer diameter of 4mm. The stretchable inflation tube is attached to the distal end of the catheter that resides within the balloon and exits the catheter just behind the balloon and is accessible for future adjustments. The inflation tube travels within the soft catheter outside of the balloon and exits where it is attached to a luer-lock valve. The valve is closed with a cap. The valve has within it a silicone piece that prevents fluid escape even when the cap is off. The balloon is filled with saline and methylene blue (in the event of a balloon deflation the urine turns blue).

### **5.1.2. Additional Components and Adjunct Devices**

The following additional items are not supplied by Spatz FGIA, but are used during the implantation, adjustment, and extraction procedures.

#### **Sterile Saline Solution**

Sterile saline solution is used to fill the balloon to the desired volume.

#### **Methylene Blue**

USP 1% methylene blue (Akorn 1% Methylene Blue Injection, NDC 17478-504-01) is added to the saline to provide a visual indicator to the patient (i.e., blue-green urine) when saline solution is released from a deflated balloon.

#### **Endoscopic Rat Tooth Grasping Forceps**

Rat tooth grasping forceps are recommended for use during the balloon adjustment and removal procedures to grab the suture loop at the top of the cap.

### **Large Polypectomy Snare**

A large polypectomy snare is used during the balloon removal procedure to grab the valve.

## **5.2. Device Labeling**

All components of the Spatz3 device will be labeled “CAUTION Investigational device. Limited by Federal (or United States) law to investigational use”. Labeling will also include the Sponsor name and contact details.

## **5.3. Device Accountability**

The study site coordinator will maintain a log for tracking study devices, and a final reconciliation of study devices will be performed at the study end. Unused devices will be returned to the sponsor. The lot number for each device will be recorded on the case report forms (CRFs).

## **6. DATA MONITORING AND SAFETY REPORTING**

### **6.1. Data Monitoring Committee**

An independent Data Monitoring Committee (DMC) will serve as an autonomous advisory group for Spatz FGIA, Inc., the sponsor of this trial. The DMC will be responsible for safeguarding the interests of trial participants, assessing the safety and efficacy of the interventions during the trial, adjudication of Adverse Events, and for monitoring the overall conduct of the clinical trial. The DMC may also provide recommendations about stopping or continuing the trial. To contribute to enhancing the integrity of the trial, the DMC may also formulate recommendations relating to the selection/recruitment/retention of participants, their management, improving adherence to protocol-specified regimens and retention of participants, and the procedures for data management and quality control.

The DMC members appointed for this trial consist of individuals who collectively have experience and expertise in the management of patients with obesity, experience in randomized clinical trials with experimental agents/devices, experience in safety monitoring and absence of significant conflicts of interest.

The first DMC meeting will occur once 25 subjects have either been implanted for at least 2 months or have terminated from the trial. Subsequent DMC meetings will be scheduled based on the following assessment of gastric ulcer rates.

At each DMC meeting, the crude rate of gastric ulcers will be calculated using as its denominator only subjects who have been implanted for at least 2 months plus all subjects implanted less than 2 months but had experienced a gastric ulcer event. A gastric ulcer is defined as a gastric lesion  $\geq 5$ mm in diameter with unequivocal depth by endoscopy. The date of the event will be the date of the confirmatory endoscopy. If this rate exceeds 10% then a Kaplan-Meier curve will be calculated that includes all implanted subjects. Subjects who are ongoing at this time without having experienced a gastric ulcer event will be censored at the data cutoff date, and subjects who terminated from the trial due to any reason other than a gastric ulcer event will be censored at the time of explant. Rates at each monthly interval for which a minimum of 25 subjects have been implanted will be calculated. For example, if 30 subjects have been implanted for at least 3 months, but only 20 for at least 4 months then rates will be calculated for 1, 2, and 3 months only.

If all of the monthly rates of gastric ulcers are below 10%, the DMC will meet every two months. If any of the monthly rates of gastric ulcers exceeds 10%, the DMC will meet every month.

A separate DMC charter will contain full details of the committee and its roles and reporting structure.

### **6.2. Adverse Events**

#### **6.2.1. Definitions**

The following definitions will be used:

##### **Adverse Event**

Any untoward medical occurrence, unintended disease or injury, or untoward clinical signs (including abnormal laboratory findings) whether or not related to the study intervention.

### **Serious Adverse Event (SAE)**

An adverse event that meets one of the following criteria

- Led to death
- Resulted in serious deterioration in the health of the subject that results in:
- Life-threatening illness or injury
- Permanent impairment of a body structure or a body function
- The need for in-patient care or prolongation of hospitalization
- Medical or surgical intervention to prevent life-threatening illness or injury or permanent impairment to a body structure or a body function.
- Planned hospitalization for a pre-existing condition, or a procedure required by the trial protocol, without serious deterioration in health, is not considered a serious adverse event.

### **Device-Related Adverse Event (DRAE)**

An adverse event related to the use of an investigational medical device. This definition includes any events resulting from insufficient or inadequate instructions for use, deployment, implantation, or operation, or any malfunction of the investigational device. This definition also includes any event resulting from user error or from intentional misuse of the investigational device.

### **Serious Device-Related Adverse Event (SDRAE)**

Any untoward medical occurrence that can be attributed wholly or partly to the device, which resulted in any of the characteristics of a serious adverse event as described above.

### **Unanticipated Adverse Device Effects (UADE)**

Any adverse device effect which, by its nature, incidence, severity or outcome, has not been identified in [Section 6.2.2](#).

### **Device Deficiency**

Inadequacy of a medical device with respect to its identity, quality, durability, reliability, safety or performance. Device deficiencies include malfunctions, use errors and inadequate labeling. Device deficiencies resulting in SAEs will be managed as detailed in [Section 6.2.3](#).

Device deficiencies that did not lead to an adverse event, but could have led to a medical occurrence if suitable action had not been taken, or intervention had not been made or if circumstances had been less fortunate will also be managed as detailed in section 8.2.3.

### **Severity Definitions**

The following definitions will be used to determine the severity rating for all adverse events:

Mild: awareness of signs or symptoms, that does not interfere with the subject's usual activity or is transient that resolved without treatment and with no sequelae.

Moderate: a sign or symptom, which interferes with the subject's usual activity.

Severe: incapacity with inability to do work or perform usual activities.

